## **5 ANALYSIS POPULATIONS**

Four (4) analysis populations will be defined and used in the statistical analyses: (1) Intent-to-treat (ITT) population; (2) modified intent-to-treat (mITT) population; (3) per-protocol (PP) population; and (4) safety population.

### **5.1 Intent-to-treat Population**

The intent-to-treat (ITT) population will include all subjects who were enrolled into the study.

### **5.2 Modified Intent-to-Treat Population**

The modified intent-to-treat (mITT) population will include all subjects who received at least one dose of study medication and had at least one follow-up visit with a completed IOP measurement.

### **5.3 Per Protocol Population**

The per-protocol (PP) population will consist of all subjects in the mITT population who completed 12 weeks of study treatment without significant protocol violations.

The following subjects will be excluded from the per-protocol population:

- No efficacy evaluation at baseline, and/or have no follow-up visit
- Used any prohibited medications during the study period that would interfere with the study objectives
- Had any prohibited procedures during the study period that would interfere with the study objectives.

Sensitivity analyses of the primary efficacy analyses will be conducted using the PP population.

### **5.4 Safety Population**

The safety population will include all subjects who received at least one (1) dose of study medication. All safety analyses will be conducted using the safety population.

## **6 STATISTICAL METHODS**

All data processing, summarization, and analyses will be performed using SAS® Version 9.4 or higher.

Unless otherwise specified, for continuous variables, descriptive statistics will include the number of subjects/eyes (n), mean, standard deviation, median, minimum and maximum values. Categorical variables will be summarized using frequency and percentages.

Unless, otherwise stated, missing data will be handled as is, except when the aforementioned dates are required for calculations, the partial dates will have either '01' or 'Jan' imputed with an exception for dates related to AEs where the date closest to the last event (visit date, etc.) should be used rather than arbitrary '01' of that month.

All efficacy data will be summarized at each time point using appropriate descriptive statistics. Summaries will be presented for the ITT, mITT and PP populations. All summaries and analyses will be performed using data pooled across centers.

Baseline assessment will be those recorded prior to dosing. In cases where more than one pre-dose observation has been recorded, the **last recording** will be identified as the baseline assessment.

Study days will be numbered relative to the study starting date (Visit 1, presumably, the first dosing date).

Recorded data will be assigned to evaluation/assessment windows. If more than one clinical evaluation is made within a window for a particular visit, the record with the date closest to the targeted window will be used except for AEs where the **worst assessment** will be used.

Visit windows and analytical windows are defined as follow:

Visit	Targeted Window	Analytical Window
Visit 1 (Baseline, First dosing date)	Day 0	Day 0
Visit 2	Week 6 ( $\pm$ 7 day)	Day 2 to Day 63
Visit 3 (End of treatment visit)	Week 12 ( $\pm$ 7 days)	Day 64 to End of Study

### 6.1 Subject Disposition

The number and percentage of subjects will be summarized for the following:

- Subjects discontinued, completed treatment
- Subjects discontinued for each reason(s)
- Subjects in the mITT population

- Subjects in the PP population
- Subjects in the safety population
- Subjects at each investigational site

Screened failures, subjects discontinued, and subject excluded from efficacy analysis will be listed, respectively.

## 6.2 Treatments

### 6.2.1 Extent of Study Drug Exposure

Exposure (i.e., treatment time, days) will be determined as following:

$$\text{Time in Study Treatment (Treatment duration)} = \text{Date of Last Dose} - \text{Date of First Dose} + 1$$

Assumedly, the Date of Visit 1 (Baseline) is the First Dose Date, and the day before Date of Week 12 Visit (End of Study) is the Last Dose Date.

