### **9.2 Subject Discontinuation**

A subject may be withdrawn from the study prior to completion for any reason and categorized as follows:

- AEs
- Lost to follow-up
- Other (administrative reasons, etc.)

If a subject discontinues from the study for any reason at any point beyond his/her Baseline Visit (Visit 1), he/she should be requested to return for a final visit at which time all Visit 3 (Week 12) procedures should be performed according to the protocol Schedule of Visits/Procedures (see [Appendix 4](#)).

Subjects who are prematurely withdrawn or discontinued from the study will not be replaced.

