### 3.2 Study Visits and Schedule of Events

Subjects will participate in the study for approximately 12 weeks. There will be a total of 3 clinic visits: Screening/Baseline (Day 0), 2 in-treatment visits at Week 6 ( $\pm 7$  days) and Week 12 ( $\pm 7$  days). Activities and medical procedures to be performed at each study visit are summarized in the study protocol Appendix 4.

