### 3.7 Adverse Events (AE)

An AE is defined as any untoward medical occurrence in a subject during the course of a study. An AE can, therefore, be any unfavorable and unintended sign (including a clinically significant abnormal laboratory finding), symptom, or disease temporally associated with the use of an investigational or marketed medicinal product, whether or not considered related to the investigational or marketed medicinal product. AEs include any illness, sign, symptom, or clinically significant laboratory test abnormality that has appeared or worsened during the course of the clinical trial, regardless of causal relationship to the study medication(s) under study.

AEs may be either spontaneously reported or elicited during questioning and examination of a subject.

The following information will be collected and tabulated for all AEs:

- AE description
- AE location (OD, OS, OU, Non-ocular)
- Start date
- Whether the AE is ongoing (Yes, No)
- End date
- Severity (Mild, Moderate, Severe. See protocol section 10.1.1 for severity definition)
- Whether the AE is serious (Yes, No)
- Whether the AE is congenital anomaly or birth defect (Yes, No)
- Whether the AE led to death (Yes, No)
- Whether the AE led to disability or permanent damage (Yes, No)
- Whether the AE led to hospitalization (Yes, No)
- Whether the AE is life threatening (Yes, No)
- Whether the AE led to other important medical event (Yes, No)
- Relationship to study treatment (Not related, Unlikely related, Possibly related, Related)
- Action taken with study treatment (Not changed, Drug interrupted, Drug withdrawn, N/A)
- Whether a concomitant or additional treatment given (Yes, No)

- Whether the AE led to study discontinuation (Yes, No)
- Whether any other action(s) taken (Yes, No. If yes, specification for other actions)
- Outcome (Fatal, Not Recovered/Not resolved, Recovered/Resolved, Recovered/Resolved with sequelae, Recovering/Resolving, Unknown)

The AEs and SAEs will be collected from visits 2 and 3 as well as upon subject report after visit 1 and will continue until the final protocol required visit and/or continue through resolution, or stabilization or the investigator assesses them as chronic or stable or the subject's participation in the trial ends, whichever occurs first.

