### 6.2.3 Treatment Discontinuation and Rescue Medications

No rescue medication is proposed in this study. The subject will be exited from the study after discontinuation from the study treatment.

Efficacy assessment collected from the treatment discontinuation exit will be mapped to the next scheduled visit and considered as observed data. (i.e., the mapping will be performed prior to any data imputation if any).

Safety assessment for the treatment discontinuation exit will not be mapped. Instead, it will be treated as the last assessment during treatment period.

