### **7.2 Study Days**

Study days will be computed for each visit and AE event.

$$\text{Study Days} = \text{Date of Visit/Event} - \text{Date of First Dose} + 1$$

Or, if the visit/event occurs prior to the Day 1

$$\text{Study Days} = \text{Date of Visit/Event} - \text{Date of First Dose}$$

Date of First Dose is the Day 1 Visit date.

Last Date in study is the Day 84 Visit or the last visit where the subject was seen by the investigator. If lost-to-follow-up, the last date of contact is the Last Date in study.

If a subject had contact with the site after the final visit (e.g. for AE follow up), the last visit date will be the Last Date in study, not the contact date.

Time in Study (Study duration) = Last Date in study – Date of First Dose + 1

Time in Study Treatment (Treatment duration) = Date of Last Dose – Date of First Dose + 1

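### SAP 6.2.1 assumes the last dose date from the final visit, so exposure is overstated or undefined for subjects who stopped early and undefined for those lost to follow-up

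*SAP*

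**What the plan says.** SAP 6.2.1 and 7.2 give the same formula: "Time in Study Treatment (Treatment duration) = Date of Last Dose – Date of First Dose + 1". Section 7.2 does not say how the last dose date is found. Section 6.2.1 supplies both dates by assumption. For the first dose it says "Assumedly, the Date of Visit 1 (Baseline) is the First Dose Date", and for the last dose that "the day before Date of Week 12 Visit (End of Study) is the Last Dose Date". No other rule for the last dose date appears in either document.

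Both documents foresee subjects who stop before Week 12. SAP 3.7 records drug interruption or withdrawal as an action taken for an adverse event. SAP 6.2.3 says "The subject will be exited from the study after discontinuation from the study treatment". Protocol 9.2 says that a subject who discontinues after Visit 1 "he/she should be requested to return for a final visit at which time all Visit 3 (Week 12) procedures should be performed". Neither section sets a time limit for that visit. Loss to follow-up is a listed reason for discontinuation in Protocol 9.2 and SAP 4.1.

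For lost subjects, SAP 7.2 takes the last contact as the last date in study. That date enters study duration, not treatment duration.

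**The concern.** An exposure summary should count days on drug. A rule anchored to a clinic visit does so only if the subject was still dosing up to that visit. A subject who stops because of an adverse event and returns later for an exit visit may have the off-drug days counted as exposure. A subject who never returns has no visit to anchor the date.

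The subjects affected are those who stopped, for whom time on drug is most informative when tolerability is described. The error also runs one way: exposure can be too long but never too short, so errors do not cancel in the mean.

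**Working it through.** The documents state no exposure figure, stopping rate or lag, so there is no planned number to reproduce. The check applies the SAP's formula.

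**Notation.** Let *s* be the days from Visit 1 to the actual last dose, and *v* the days from Visit 1 to the final visit. The first dose is on the Visit 1 date (SAP 6.2.1).

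- By the rule: last dose at *v* − 1, so exposure = (*v* − 1) − 0 + 1 = *v*.
- Actual: exposure = *s* − 0 + 1 = *s* + 1.
- Excess = *v* − (*s* + 1) = (*v* − *s*) − 1, that is, the lag minus 1 day.

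Dosing is in the evening, so the last dose before a clinic visit is at the latest the evening before. Hence *s* ≤ *v* − 1 and the excess is zero or positive.

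**Subjects on drug to the end.** Final visits at 77, 84 and 91 days (12 weeks ± 7 days) give 77, 84 and 91 days of exposure. The rule is right for them.

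**Subjects who stopped earlier** (*s* and *v* are illustrations):

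| Last dose *s* | Final visit *v* | Rule | Actual | Excess |
|---|---|---|---|---|
| 14 | 15 | 15 | 15 | 0 |
| 14 | 21 | 21 | 15 | 6 |
| 19 | 33 | 33 | 20 | 13 |
| 20 | 42 | 42 | 21 | 21 |
| 42 | 84 | 84 | 43 | 41 |
| 20 | 84 | 84 | 21 | 63 |

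In the third row the last dose is on study Day 20 (SAP 7.2 counts the first dose as Day 1) and exit is 14 days later. The excess is 13 days, and 13/20 = 65%.

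**Which rows can arise.** The wording in 6.2.1 names the Week 12 visit and adds End of Study in brackets.

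- *Any exit visit.* Protocol 9.2 gives the exit visit all the Visit 3 procedures, which favours this reading. Every row can then occur.
- *Week 12 only.* SAP 4.1 treats completing the Week 12 visit as study completion and everyone else as discontinued, which favours this reading. The first four rows then have no last dose date. Only the last two, where drops stopped but the subject still attended Week 12, are overstated.

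**Lost to follow-up.** No last dose date exists on either reading. SAP 6 leaves missing data as they are, and its partial-date rule only completes dates that were partly recorded. Plausible exposure runs from about 42 to 84 days for a subject lost after Visit 2, and from about 1 to 42 days for one lost after Visit 1 and before Week 6.

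**Effect on the mean, under the any-exit reading.** Shift = share of early stoppers × mean excess.

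- 10% stopping, 14-day lag: 0.10 × 13 = 1.3 days.
- 20% stopping, 14-day lag: 0.20 × 13 = 2.6 days.
- Wider range, 5% to 20% stopping with mean excess of 7 to 42 days: 0.05 × 7 = 0.35 days up to 0.20 × 42 = 8.4 days.

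Against 84 days, 1.3 to 2.6 days is about 1.5% to 3.1%. All shares and lags are assumptions.

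**The case against.** The strongest reply is that the sentence is worded as an assumption and may be only a default for subjects who attend Week 12. The SAP is to be read with the case report form and its Module II, neither of which is among the documents, so a last dose date may already be collected. This stands in part. It cannot be shown that the field is missing, or that a recorded date would be discarded for every subject. But the SAP nowhere says that a recorded date takes precedence, and a programmer following 6.2.1 as written would use the visit.

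The lag may also be short, since SAP 6.2.3 exits subjects after they stop treatment. The excess is zero if the exit visit falls the day after the last dose. That is fair, though no deadline is set.

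Exposure also feeds no other stated analysis. Adverse event denominators in SAP 6.6.1 are eyes or subjects, no exposure-adjusted rate is planned, and the primary IOP endpoint does not use it. This stands and limits the point.

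A reader might go further and infer that the assumed date also closes the period for treatment-emergent events, or lets subjects who stopped drops pass into the per-protocol population. The documents do not support either inference:

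- SAP 4.5 defines treatment-emergent events by onset on or after the first dose, with no end date. Section 6.6.1 mentions a treatment period but does not tie it to 6.2.1. Section 6.2.3 counts the discontinuation exit assessment as the last within that period, not the day before it.
- SAP 5.3 sets its own requirement of 12 weeks of treatment without significant violations and does not cite 6.2.1. The exit rule, the recorded action for adverse events, the deviation listing and the returned bottles could all reveal stopping.

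**Conclusion.** The point holds as a minor defect confined to the exposure summary. SAP 6.2.1 states a rule that, followed literally, gives exposure too long by the lag minus 1 day for subjects who stopped before the visit it refers to, and gives no value for lost subjects. For early exits the ambiguous wording decides whether the fault is overstatement or a missing date; neither reading is satisfactory.

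For one subject the excess can be large (0 to 63 days in the illustrations). For the overall mean it is probably small. The figure of 1.3 to 2.6 days rests on an assumed 10% to 20% stopping, an assumed 14-day lag, and the any-exit reading. The documents do not show any effect on the primary endpoint, adverse event incidence or the definition of the analysis populations.

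**What to change.** Amend SAP 6.2.1 to say:

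1. For any subject who stopped before the final visit, use the actual last dose date, as recorded on the case report form or the End of Study form. Protocol 9.0 already requires that form for completed and discontinued subjects; add the date field if it is not there.
2. Keep the day-before-visit rule only for subjects still on drug at Visit 3.
3. For subjects lost to follow-up, use the last date known to be on drug.
4. Report how many last dose dates were imputed, and by which rule.

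Item 3 gives a lower bound on exposure, which is one reason to report the count in item 4. No change to SAP 5.3 or 6.6.1 is needed on this account.

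The cost is at most one date field and a few lines of SAP text. Visits, procedures and treatment are unchanged.

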### 6.2.2 Concomitant Medications

Prior and concomitant medications will be presented for each subject coded per the World Health Organization (WHO) Drug dictionary (WHO Drug Sept 2018 version at the time of SAP publication, or the current version when superseded). When two medications are coded to the same preferred term, both will be counted.

The data will also be summarized by drug class and by preferred term, and by ocular-specific and non-ocular specific drugs. Medications will be ordered alphabetically by preferred term.

Medications with partial dates that do not allow determination of whether prior or concomitant will be considered concomitant.

Subject listing of prior and concomitant medication will be presented.

### 6.2.3 Treatment Discontinuation and Rescue Medications

No rescue medication is proposed in this study. The subject will be exited from the study after discontinuation from the study treatment.

Efficacy assessment collected from the treatment discontinuation exit will be mapped to the next scheduled visit and considered as observed data. (i.e., the mapping will be performed prior to any data imputation if any).

Safety assessment for the treatment discontinuation exit will not be mapped. Instead, it will be treated as the last assessment during treatment period.

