### 4.3 Primary Efficacy Endpoints

The primary efficacy measure is the intraocular pressure (IOP, mmHg). The primary efficacy endpoint is the percent (%) IOP reduction from baseline.

The primary efficacy analysis will be performed for mITT and PP populations. There will be no imputation for missing Week 12 assessment.

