### 6.5.2 Exploratory/Other Assessments

### 6.5.3 Sensitivity Analysis

Analyses on the primary efficacy outcome will be performed using the PP population.

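### Do the exit-mapping rule in SAP 6.2.3 and the analytical windows in SAP 6 leave the Week 12 IOP of early discontinuers undefined?

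*SAP*

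**What the plan says.** SAP 6.2.3 (Treatment Discontinuation and Rescue Medications) gives the specific rule: "Efficacy assessment collected from the treatment discontinuation exit will be mapped to the next scheduled visit and considered as observed data". It adds that this step comes before any imputation. Safety data are handled the opposite way: "Safety assessment for the treatment discontinuation exit will not be mapped".

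SAP 6 (Statistical Methods) gives the general rule: "Recorded data will be assigned to evaluation/assessment windows". Visit 2 takes Days 2 to 63 and Visit 3 takes "Day 64 to End of Study". When a window holds more than one record, "the record with the date closest to the targeted window will be used except for AEs". The section also says "All efficacy data will be summarized at each time point using appropriate descriptive statistics", so a Week 12 result will be reported even though the primary endpoint names no time point.

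On missing data, SAP 4.3 says for the mITT and PP analyses: "There will be no imputation for missing Week 12 assessment". Protocol 11.3.2 adds an ITT analysis that fills a missing Week 12 value by carrying Week 6 forward. The only sensitivity analysis visible is in SAP 6.5.3: "Analyses on the primary efficacy outcome will be performed using the PP population". SAP 5.3 limits that population to subjects who completed 12 weeks of treatment.

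Protocol 9.2 asks every subject who discontinues after baseline to return for a final visit at which all the Visit 3 procedures are done.

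**The concern.** The two SAP sections assign the same reading by different principles, and neither cites the other. The window rule is written as universal. The only order that 6.2.3 gives is mapping before imputation, which says nothing about windowing.

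If the windows prevailed, a subject who attended Visit 2 and left a week or two later would have no Week 12 value in mITT, and the Week 6 value in ITT with carry-forward. If the mapping prevailed, the exit reading would be the Week 12 value in both. Percent IOP reduction is the primary variable, so two programmers could in principle derive different primary data for the same subject.

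There is a second worry even if mapping prevails. Readings taken weeks early enter the Week 12 summary as observed, with no visible flag, and the PP analysis removes all discontinuers rather than isolating these readings.

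**Working it through.** The plan states no figure to reproduce, so the check is to apply both rules day by day. Inputs: Visit 2 at Week 6 ± 7 days (Days 35 to 49), Visit 3 at Day 84, analytical cut between Days 63 and 64 (all SAP 6), with baseline as Day 0 as in the window table.

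| Exit timing | SAP 6.2.3 mapping | SAP 6 windows | Agree? |
|---|---|---|---|
| From Day 2, Visit 2 not yet attended, up to Day 49 | Week 6 | Week 6 | Yes |
| Visit 2 attended, exit later and up to Day 63 | Week 12 | Visit 2 window; Week 12 empty | No |
| Visit 2 missed, exit about Days 50 to 63 | Week 12 | Week 6 | No |
| Day 64 onward | Week 12 | Week 12 | Yes |

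**Span of disagreement.** With Visit 2 attended on day v, the exit days in dispute number 63 − v: 28 for v = 35, 21 for v = 42, 14 for v = 49. Over all fifteen possible Visit 2 days this gives 15 × (28 + 14)/2 = 315 day pairs. A mapped reading in the span is 84 − 63 = 21 to 84 − 36 = 48 days early.

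**What changes in each analysis.**
- Un-imputed mITT or ITT: all 315 pairs differ, as an observed value against a missing one.
- ITT with carry-forward, taking closest to mean closest to Day 42: in 1 + 3 + 5 + 7 + 9 + 11 + 13 = 49 pairs the exit is nearer to target than Visit 2, so it becomes the Week 6 value and is carried forward, giving the same result as mapping. Seven pairs tie. The other 315 − 49 − 7 = 259 differ.
- Visit 2 missed: the carry-forward Week 12 value is the exit reading under either rule.
- PP: no effect, since discontinuers are excluded.

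**Illustration with assumed IOPs.** Baseline 24, Visit 2 on Day 42 at 18, exit on Day 55 at 22 mmHg. The Week 6 reduction is (24 − 18)/24 = 25.0%; the exit reduction is (24 − 22)/24 = 8.3%. Mapping gives Week 12 = 8.3%. The windows give missing in mITT and 25.0% in ITT with carry-forward. If a fraction f of 250 subjects were such exits and everyone else had a 25% reduction, the mean would differ by f × 16.67 points: 0.33 at f = 2%, 0.83 at 5%, 1.67 at 10%.

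**Which rule governs.** In the first and last rows of the table the mapping sentence changes nothing. Setting aside an exit on Day 1, which no window covers, the two middle rows are the only place where it can act. If the windows governed there too, the sentence would be empty, and so would its contrast with unmapped safety data. Mapping a reading to the next visit means moving it from where its date would put it. Protocol 9.2 fits this, since the exit visit is run as a Visit 3. Once the exit reading is at Week 12 it is no longer in the Visit 2 window, so it cannot displace an attended Visit 2 record.

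**Day numbering.** The window table calls baseline Day 0; the formula in SAP 7.2 makes the first-dose date Day 1. A reading 63 days after baseline is therefore Day 63 (Visit 2) or Day 64 (Visit 3), and at the lower edge a reading on the day after baseline falls outside or inside the Visit 2 window. The upper edge is midway between the targets, 63 − 42 = 84 − 63 = 21 days, and 14 days outside either visit's permitted range (Day 49 and Day 77). Baseline is not lost, because SAP 6 defines it separately as the last pre-dose record.

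**The case for a change.** The strongest case for a change is that precedence is inferred, not stated. Matching two programmers' datasets exposes a disagreement but supplies no rule for settling it, and it exposes nothing if both choose the windows. In an open-label study such choices should be fixed before the data are seen, and the remedy is cheap: a sentence or two, a flag and one table.

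Part of this stands. There is no cross-reference, and the Day 0/Day 1 mismatch is a genuine slip. But the inference is close to forced, because the other reading leaves 6.2.3 without a function. A precedence sentence would therefore record what analysts already have to do.

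The proposed extra table, excluding mapped readings taken before Day 64, adds little. The PP analysis already shows the primary variable with every discontinuer removed, and the extra table would still keep exits on Days 64 to 76, which are 8 to 20 days early under either rule. Whether an exit IOP should count as observed at Week 12 can be debated, but it is a stated, prespecified choice. Dropping those readings would take these subjects out of the un-imputed Week 12 summary.

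Early readings can also be traced: SAP 6.1 lists discontinued subjects, and SAP 7.4 puts visit dates and relative days in the listings where applicable. SAP 1 places the table layouts in a separate Module II, which is not among these documents, so it cannot be said that the tables will hide early exits.

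**Conclusion.** No change to the plan follows. The two rules do diverge on paper, for 14 to 28 exit days after an attended Visit 2 and for about Days 50 to 63 when Visit 2 was missed. Read as a whole, however, the SAP allows only one workable order: exit mapping first, windows for everything else. That already gives the result a clarifying sentence would ask for. This is a missing cross-reference that analysts fill sensibly, and the exact-match requirement in SAP 9 acts as a check on a split reading. The day-numbering mismatch is a clerical slip confined to readings at the window edges.

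The stakes are also limited. The visible efficacy analysis is descriptive and single-arm, with no comparison between therapy groups. The shifts of 0.33 to 1.67 points rest wholly on assumed IOPs and on 2% to 10% of all subjects falling in a narrow interval and returning for a reading; the documents give nothing from which to estimate either. The conclusion rests on taking 6.2.3 as a rule meant to have an effect.

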### 7.7 **Unscheduled Visits**

In the event a subject returns for an unscheduled visit, the investigator (or designee) will perform/administer necessary assessments. Information collected from an unscheduled visit will be reported on Interim/Unscheduled Visit CRF(s).

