#### **6.6.2 Other Safety Assessments**

Frequency and percent of subjects/eyes with findings on visual acuity, blood pressure and biomicroscopy will be summarized for each visit.

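### Eye and blood-pressure examinations at a discontinuation exit reach no visible summary table, and the closest-to-target rule usually drops problem-driven unscheduled ones

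*SAP*

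**What the plan says.** Protocol 9.2 asks that a subject who stops after baseline be requested to return and have every Visit 3 procedure. Protocol 7.6 lists visual acuity, biomicroscopy and blood pressure among them. Protocol 7.7 has unscheduled-visit results entered on their own case report form.

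SAP 6.2.3 treats the two kinds of exit data differently. For efficacy: "Efficacy assessment collected from the treatment discontinuation exit will be mapped to the next scheduled visit and considered as observed data". For safety: "Safety assessment for the treatment discontinuation exit will not be mapped. Instead, it will be treated as the last assessment during treatment period".

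SAP 6.6.2 is the only visible summary of the examinations: "Frequency and percent of subjects/eyes with findings on visual acuity, blood pressure and biomicroscopy will be summarized for each visit". No visible section plans a summary of the last assessment or of the worst value on treatment.

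SAP section 6 gives a general rule: "Recorded data will be assigned to evaluation/assessment windows". Visit 2 covers Day 2 to Day 63. Visit 3, which the window table also labels the end-of-treatment visit, covers "Day 64 to End of Study". If several records share a window, "the record with the date closest to the targeted window will be used except for AEs", for which the worst assessment is taken.

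**The concern.** The examinations at risk are not a random subset. Exit examinations belong to subjects who stopped, and adverse events are one of the withdrawal categories in Protocol 9.2. Unscheduled examinations tend to belong to subjects who came in with a complaint. If these fall out of the tables, the by-visit percentages mainly describe subjects who stayed on treatment and attended on schedule.

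This matters because the study has a single arm, so absolute rates are the safety result. SAP 6.6 names visual acuity, eye examinations and biomicroscopy, beside adverse events, as the basis for judging safety and tolerability. The handling is also uneven within SAP 6.2.3: a discontinued subject's IOP enters the efficacy table, while the slit-lamp examination from the same exit visit has no row.

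**Working it through.** The plan states no figure to reproduce: SAP 3.3 says that no sample size calculation was done, and neither document gives a dropout rate or a finding rate. The check has two parts.

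**1. Which examinations reach a by-visit row?** Inputs are the SAP section 6 windows, with targets taken as Day 42 (6 × 7) and Day 84 (12 × 7), and the record nearest the target day kept.

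| Examination | Exit not mapped (SAP 6.2.3) | Exit placed by window (SAP 6) |
|---|---|---|
| Exit Day 20, before Visit 2 | no row | Visit 2 |
| Exit Day 55, after Visit 2 on Day 42 | no row | no row (13 days from target against 0) |
| Exit Day 70, after Visit 2 on Day 42 | no row | Visit 3 |

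So the two sections give different answers for Day 20 and Day 70, and under either one the Day 55 exit is left out.

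Unscheduled examinations are not covered by SAP 6.2.3, so only the window rule applies:

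| Unscheduled examination | Result |
|---|---|
| Day 20, Visit 2 on Day 42 | dropped (22 days from target against 0) |
| Day 65, Visit 3 on Day 84 | dropped (19 days against 0) |
| Day 20, Visit 2 missed | used as Visit 2 |
| Day 43, Visit 2 on Day 49 | used instead of the scheduled visit (1 day against 7) |
| Day 65, then lost to follow-up | used as Visit 3 |

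The Day 43 case depends on measuring distance to the target day. Both dates lie inside the ±7-day targeted window (Day 35 to Day 49), so measured to that window they would tie. The other results are the same either way.

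**2. How much could it change a rate?** Let d be the share of subjects who exit early, p_c the finding rate at Week 12 among completers, and p_e the rate at the exit examination. The Week 12 row without exits shows p_c. With exits counted it is (1 − d) × p_c + d × p_e, so the gap is d × (p_e − p_c). All rates below are assumptions; N = 250.

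| d (subjects) | p_c = 20%, p_e = 40% | p_c = 20%, p_e = 60% | p_c = 5%, p_e = 20% | p_c = 5%, p_e = 40% |
|---|---|---|---|---|
| 5% (13) | 21.0% | 22.1% | 5.8% | 6.8% |
| 10% (25) | 22.0% | 24.0% | 6.5% | 8.5% |
| 20% (50) | 24.0% | 28.0% | 8.0% | 12.0% |

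The p_c = 20% columns use whole subjects, for example (225 × 20% + 25 × 40%) / 250 = 22.0%. The p_c = 5% columns use proportions, for example 0.90 × 5% + 0.10 × 20% = 6.5%. If p_e = p_c, the gap is zero.

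These figures assume that every early exit is examined. If only a fraction r return, the rate is [(1 − d) × p_c + d × r × p_e] / [(1 − d) + d × r], which falls back to p_c as r goes to 0. They also concern only the last examination: a subject who exits after Week 6 already appears in the Visit 2 row. They do not size the unscheduled-visit problem.

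**The case against.** The strongest reply is that the plan may already have a row for the exit examination. The window table calls Visit 3 the end-of-treatment visit and runs it to the end of the study, so the last assessment during treatment could mean that row. SAP section 1 also refers to Module II for tables and listings, and a suitable row may exist there. This is fair, and it means that exclusion is not proven. But SAP 6.2.3 says that these data are not mapped, in direct contrast to the efficacy data, and nothing visible says which row they feed. The ambiguity has to be settled: SAP section 9 requires two independently programmed datasets to match fully.

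A second reply is that the signal is captured elsewhere. The adverse event definition includes signs elicited on examination. Ocular events are counted per eye at highest severity, and events leading to discontinuation are tabulated (SAP 6.6.1). Listings support the tables (SAP 7.4), and Protocol 11.3.3.2 allows other safety variables to be listed rather than summarized. This stands as a partial offset. A listing gives no rate, however, and a graded finding reaches the adverse event tables only if it is recorded as an event.

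A third reply is that by-visit tables in a descriptive phase 4 study describe attendees and do not claim cumulative incidence. That is true, and it limits the weight of the point.

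A reader might go further and infer that unscheduled examinations have no place in the tables at all. The documents do not support that: the SAP does not exclude them, the windows are continuous from Day 2, and such an examination is used when no other record in its window is nearer the target.

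**Conclusion.** The point holds for discontinuation exits. As SAP 6.2.3 and 6.6.2 are written, the Visit 3 examination requested from subjects who stop enters no visible summary table, and SAP 6.2.3 and section 6 disagree on where it belongs. For unscheduled visits the narrower point holds: with the worst-assessment exception limited to adverse events, a problem-driven examination is lost whenever the scheduled visit falls nearer the target.

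The by-visit tables may therefore understate on-treatment findings. Under the assumed rates the Week 12 figure would move by 0.8 percentage points (5% exits, finding rates 5% and 20%) to 8 points (20% exits, rates 20% and 60%), and not at all if exits resemble completers. Incomplete attendance at exit would make the gap smaller. It would be wrong to infer that the findings vanish from the study report, since adverse event tables and listings remain. The conclusion also rests on Module II not already containing a suitable row. It is a worthwhile correction to the plan and does not affect the primary efficacy analysis.

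**What to change.** 1. Reconcile SAP 6.2.3 with the section 6 windows: state whether exit safety examinations enter a visit window, and which output uses the last assessment during treatment.
2. In SAP 6.6.2, keep the by-visit rows as they are and add two rows in the Safety population: *worst post-baseline value* and *last on-treatment value*. Present them per eye for visual acuity and biomicroscopy and per subject for blood pressure, and draw on all scheduled, unscheduled and exit examinations.
3. Check that the Module II shells carry the same rows.

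The cost is SAP wording and two extra rows per table; no new data are needed. The worst-value rate can only equal or exceed the by-visit rates among the same subjects. The last-value row can move either way, because exit examinations may show more or fewer findings than Week 12.
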